### ***Summative Evaluation of Program Effectiveness***

**Aim 1:** Evaluate the effect of SMAs and SMAs+P2P on diabetes patients' glycemic control, systolic blood pressure, anti-hypertensive use, statin use, and insulin starts at 6 and 12 months post-enrollment.

**Aim 2:** Assess the impact of SMAs and SMAs+P2P on service utilization and patient-centered outcomes at 6 and 12 months post-enrollment.

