We will use a mixed methods approach to our data collection and analyses. Summative data for Aims 1 and the service utilization outcomes in Aim 2 will be obtained from VA databases and will include data on clinical outcomes and service utilization, which will be measured at baseline, at 6 months, and over a period of 12-18 months post-enrollment. Because this is an implementation study, we intend to use clinical data wherever possible, rather than add to staff burden with the imposition of additional collection of data solely for research purposes—especially when data on the clinical measures of interest are already collected as part of patient care. For two of the arms (SMA, SMA+P2P), we expect labs to be drawn at baseline and 6 months through SMA staff as part of usual care. In usual care without SMAs, we may have more missing values for A1cs, although guidelines recommending checking A1cs at least every 6 months in patients with poor glycemic control.

Data on patient-centered outcomes (Aim 2) will be obtained from surveys of all participants who are scheduled to participate in SMAs and agree to participate in the study at the five sites to allow for comparisons across the SMA and SMA + P2P groups. We will collect laboratory and service utilization data on patients in all three treatment groups. Qualitative data on organizational factors likely to affect P2P program implementation will be obtained via semi-structured interviews prior to implementation, mid-implementation (7-10 months following program implementation at each site), and post-implementation (18-24 months following program implementation at each site) as part of Aim 3. To further look into the SMA sustainment efforts in Ann Arbor, additional staff interviews, staff meeting observations, and SMA observations will be conducted in Ann Arbor only. Data on staff time required for implementation of P2P will also be collected throughout the study to calculate the overall cost of program implementation (Aim 4).

Patient enrollment will take place for 18 months at the five sites. Patients receiving P2P can stay in the P2P program as long as they wish (while the program is being funded).

VA patient research procedures include completion of three surveys (baseline, 6 months post-enrollment, and 12 months post-enrollment) and collection of medical record data from VA databases. Additionally, a subset of participants will be asked to participate in interviews as part of the program evaluation.

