## **5.3 Informed Consent Procedures**

### *Informed Consent will not be sought for*

- *Veterans randomly selected from those who have not been asked to participate in SMAs (inactive controls). There will be no contact with this group.*
- *Veterans who are invited to participate in SMA or P2P but elect not to (declined participation group). We would like to ask them a few questions at the time that they elect not to participate or soon after by telephone in order to better understand the barriers to participating in the program. (Appendix 3, Refuser Questions)*

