Aim 2 (Assessment of the impact of SMAs and SMAs+P2P on service utilization and patient-centered outcomes, including patients' satisfaction with VA care, diabetes-specific quality of life and social support at 6 and 12 months post-enrollment). In our analysis of changes in patient-centered outcomes as reported on patient surveys, we will conduct a paired Wilcoxon signed rank test to determine if there are significant changes between baseline and the 6- and 12-month post-enrollment evaluation periods. We will use the Benjamini-Hochberg (BH) procedure to attempt to control the false discovery rate due to the multiple comparisons. There were very few participants in the SMA+P2P group chose to be formally matched with another participant in their SMA to give and receive peer support outside the SMA. If we do not have sufficient sample size of participants in P2P, we will be unable to compare outcomes between the SMA-only and SMA+P2P arms. In that case, will only conduct our primary analysis that combines the two SMA groups (SMA-only and SMA+P2P) into one active treatment group and compare clinical outcomes of participants participating in SMAs with those in usual care.

Fidelity of the P2P Program. To collect data on fidelity, checklists of key content areas to cover and communication skills that should be used will be completed and forwarded to Ann Arbor. A HBC or another qualified health behaviorist will attend the first P2P visit (immediately following the first SMA) and will complete a fidelity assessment checklist. Additionally, they will provide feedback to the P2P facilitator immediately following the session. This feedback will be documented and shared with the Ann Arbor study team. An assessor will continue to attend drop-in sessions, completing fidelity assessments and providing feedback, until he/she feels the P2P facilitator is ready to continue without assistance. Then the fidelity assessments will be completed approximately every 3rd drop-in session for the remainder of the study. Additionally, the P2P facilitators will be asked to complete self-assessment checklists after each session which will be forwarded to Ann Arbor.

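### Aim 2 promises the impact of SMAs on satisfaction, diabetes quality of life and social support, but the surveys have no usual-care arm and the named test shows only change

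*Combined protocol and SAP*

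**What the plan says.** The aim is causal. Section 3.0 (Summative Evaluation of Program Effectiveness) states Aim 2 as: "Assess the impact of SMAs and SMAs+P2P on service utilization and patient-centered outcomes at 6 and 12 months post-enrollment". Section 5.6.1 repeats it as "Assessment of the impact of SMAs and SMAs+P2P on service utilization and patient-centered outcomes" and names satisfaction with VA care, diabetes-specific quality of life and social support.

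The survey data come from one side only. Section 5.1.1 takes them from "surveys of all participants who are scheduled to participate in SMAs and agree to participate in the study at the five sites", and gives the purpose as "to allow for comparisons across the SMA and SMA + P2P groups". What is gathered in every group is narrower: "We will collect laboratory and service utilization data on patients in all three treatment groups". Of the usual-care controls, Section 5.3 says: "There will be no contact with this group". Section 5.5 confines their data to a pull from VA databases.

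For changes in the survey outcomes, Section 5.6.1 names one test: "we will conduct a paired Wilcoxon signed rank test to determine if there are significant changes between baseline and the 6- and 12-month" evaluations, with a Benjamini-Hochberg adjustment for multiple comparisons. The same section says that SMA-only and SMA+P2P cannot be compared if too few patients take up P2P. The analysis would then pool the two SMA groups and compare clinical outcomes with usual care.

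**The concern.** A paired test of baseline against follow-up asks whether scores moved in the people surveyed. The impact of SMAs is the difference between how scores moved and how they would have moved without SMAs. Nothing in the survey data informs the second quantity, so the stated analysis cannot answer the stated aim.

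The gap matters because the study is meant to inform wider dissemination in VHA. A significant before-after change, reported under an aim worded as impact, could be taken as evidence that SMAs improve satisfaction, quality of life or support. The data could not separate that from change that would have occurred anyway.

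**Working it through.** **Step 1. Which outcomes have a comparator.**

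| Outcome | Usual-care data? | Analysis named in 5.6.1 |
|---|---|---|
| A1c, SBP | Yes, VA records | Mixed-model difference-in-differences |
| Insulin and statin starts, anti-hypertensive class changes | Yes, VA records | Multilevel logistic and Poisson models |
| Service utilization | Yes, VA records | Two-sample Mann-Whitney test |
| Survey outcomes | No | Paired signed-rank test within participants |

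Only the last row lacks an arm without SMAs.

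**Step 2. Whether another part of the plan supplies one.**
- The Benjamini-Hochberg procedure limits false claims of change across several tests. The gap here is a missing comparator, not multiplicity.
- The SMA versus SMA+P2P comparison intended in Section 5.1.1 has no survey test named and may be dropped. If run, both arms receive SMAs, so it could show at most the increment from P2P.
- The pooled fallback against usual care covers clinical outcomes only.

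**Step 3. Illustration of size.** The plan gives no significance level, effect size, SD or power for the survey outcomes, so there is no figure of its own to reproduce.

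Input from the documents: a minimum of 560 active-treatment patients (Sections 5.2 and 5.6.2).

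Assumptions: two-sided 5% level before the Benjamini-Hochberg step; independent, normally distributed change scores; 50%, 70% or 100% returning both surveys, giving n = 0.5 × 560 = 280, 0.7 × 560 = 392, and 560; no SMA effect, but a drift d in SDs of the change score.

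The probability that the signed-rank test is significant, using its efficiency of 3/π ≈ 0.955 relative to the t-test, is approximately

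Φ(d√(0.955n) − 1.96) + Φ(−d√(0.955n) − 1.96).

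Example: n = 392 and d = 0.10 give √(0.955 × 392) ≈ 19.35. Then 1.935 − 1.96 = −0.025, Φ ≈ 0.49, and the second term is negligible.

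| Drift d | n = 280 | n = 392 | n = 560 |
|---|---|---|---|
| 0 | 5% | 5% | 5% |
| 0.05 | 13% | 16% | 21% |
| 0.10 | 37% | 49% | 64% |
| 0.20 | 91% | 97% | over 99% |

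A simulation of the signed-rank test (1,500 runs per cell) agreed to within about 2 percentage points in these cells.

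**Step 4. The same drift with a comparator.** Simulating a two-group Mann-Whitney test on change scores, with 560 per group and an equal drift of 0, 0.10 or 0.20 SD in both groups, gave rejection rates of 4.7%, 5.3% and 5.3%. The signed-rank test is sound for whether scores changed. Attribution to SMAs is what needs the second group.

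**The case against.** The strongest reply is that Section 5.6.1 describes an analysis of changes and tests for changes, which it does correctly. A reader might infer that any drift would be reported as an SMA effect. The documents do not support that: no reporting rule says so, and the causal reading comes from the wording of the aim. Nor would every drift reach significance; at 0.10 SD and n = 392 it is about an even chance.

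A reader might also take regression to the mean as established, because patients enter with poor glycemic control. Selection is on HbA1c, not on the survey scales, and the documents give no correlation between them, so this is possible but not shown. Incomplete return of surveys mainly limits to whom the result applies; it does not by itself create change within those who returned both.

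It might be tempting to replace the signed-rank test with a repeated-measures model. That is a separate trade-off over missing surveys and means versus ranks, and it leaves the missing comparator as it is. A rank test is defensible for survey scales.

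Finally, the primary A1c outcome, the other clinical outcomes and utilization all have usual-care data. This limits the point to the survey part of Aim 2. It does not remove the mismatch there.

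**Conclusion.** The concern holds for the survey outcomes of Aim 2. As planned, the data can identify uncontrolled change among SMA participants who returned surveys, but not the impact of SMAs against usual care. This follows from who is surveyed and what is tested, and does not depend on the arithmetic.

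The arithmetic shows only how readily an unrelated drift could reach significance: about 37% to 64% of the time at 0.10 SD, and 91% to over 99% at 0.20 SD, for n from 280 to 560. It does not show that a drift of either size is likely here. It rests on assumed return rates, drift sizes and significance level, and it ignores both the Benjamini-Hochberg step and clustering within SMA groups.

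**What to change.** In Section 5.6.1 under Aim 2, and for the survey part of Aim 2 in Section 3.0:

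- State that the survey analysis estimates uncontrolled change among SMA participants who returned surveys, and will not be reported as an impact of SMAs versus usual care.
- Keep claims of impact versus usual care for service utilization and clinical outcomes, where controls have data.
- If SMA+P2P and SMA are compared on the survey outcomes, limit the between-arm claim to that contrast.

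This needs no new data, no contact with controls and no change of test. The cost is a weaker survey conclusion: the study could say that participants' scores changed, but not that SMAs caused the change.

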The patients who elect to participate in the SMAs will be asked if they are interested in participating in the study. If they are interested in the study, they will be asked to sign a HIPAA authorization to collect their medical record data and link it to survey information collected as part of the study in order to evaluate the SMA program. Even if they decide not to participate in the evaluation, they can still participate in the programs. Those who are interested in the study will be sent a BL Packet Letter, the Study Info Letter, a HIPAA authorization, and the baseline survey. Participants will be asked to return the baseline survey (with a waiver of written informed consent) prior to attending their first SMA, and the signed HIPAA authorization prior to the study team linking medical record data to the survey data. The RC may call participants who have not returned the baseline survey and/or HIPAA prior to the first SMA. Whenever possible, the RC will attend the first SMA in order to administer/collect any outstanding baseline surveys and/or HIPAAs and distribute incentives for completion. Depending upon what type of group is starting at the time the participants are starting SMAs, they will become part of the **SMA group** or the **SMA + P2P group**.

Follow-up surveys, along with a pre-stamped business reply envelope, will be mailed to participants at 6-months and 12-months after their first SMA. Participants who do not return a completed survey will be mailed a second survey 2 weeks after the initial mailing. RAs may follow up by phone with participants who have outstanding surveys.

A random sample of the participants who participate in the P2P program, stratified by participation level, will be asked to participate in a semi-structured telephone interview to better understand their experiences with the program. At the end of the program, patients will be stratified by participation level: the **low participation group** (began the intervention but completed fewer than 25% of weekly phone calls/group sessions in 12 months of program participation); **moderate participation group** (completed approximately 50% of weekly phone calls/group sessions); and the **significant participation group** (completed greater than 75% of weekly phone calls/group sessions). Study staff will attempt to interview, by phone, an equal number of participants in each of these 3 groups.

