We will conduct a "difference-in-differences" (DID) analysis on our primary A1c outcome using a multilevel linear mixed effect model. The model will include an indicator of treatment, an indicator for time, the treatment-time interaction (DID estimator), and variables to adjust for baseline A1c, age, gender, and race. Random intercepts to include will be for patients (level-1) nested within site (level-2). An identical analysis will be used for the secondary SBP outcome. In the secondary analyses of insulin and statin starts, we will implement a multilevel logistic regression model, and for anti-hypertensive medication class changes, we will implement a multilevel Poisson regression model. To analyze the 6- and 12-month differences in utilization measures between treatment groups, we will use a two-sample Mann-Whitney U test. Vargha and Delaney's A statistic will be used to describe the effect size of the Mann-Whitney test. As a robustness check, we will repeat the above analyses on a subset of patients who will be matched 1:1 based on propensity scores. The propensity score model will be developed using a logistic regression on the patient demographics. Although our initial analyses will use observed data, because we are relying on data available in the EHR, we anticipate more missing values than if this were an efficacy trial. Accordingly, we will use logistic regression to model patients' likelihood of having outcome data and defined strata within which outcome values were missing at random. We will then stratify patients according to these propensities and randomly sample from the observed outcome distribution and impute these values for missing data within each stratum. As a sensitivity analysis for the primary A1c outcome, we will impute the missing data such that any missing A1c measurements at 6 or 12 months will match the value at baseline.

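### The Aim 2 survey test uses complete baseline and follow-up pairs only, with no stated handling of unreturned surveys, so selective return can bias the before-after result in either direction

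*Combined protocol and SAP*

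**What the plan says.** All of this is in the combined protocol and SAP.

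- **Survey test.** Section 5.6.1, Aim 2: "we will conduct a paired Wilcoxon signed rank test to determine if there are significant changes between baseline and the 6- and 12-month" evaluations. The only accompanying step concerns multiplicity: "We will use the Benjamini-Hochberg (BH) procedure to attempt to control the false discovery rate due to the multiple comparisons". The paragraph states no rule for missing surveys, no responder comparison and no sensitivity analysis.
- **Who is surveyed.** Section 5.1.1: the data are "obtained from surveys of all participants who are scheduled to participate in SMAs and agree to participate in the study". Section 5.3 says of the usual-care controls: "There will be no contact with this group".
- **How follow-up surveys are collected.** Section 5.2, Data Pull: they "will be mailed to participants at 6-months and 12-months after their first SMA". Non-return is foreseen: "Participants who do not return a completed survey will be mailed a second survey 2 weeks after the initial mailing". Telephone follow-up is optional, and a $10 gift card goes out with each follow-up survey.
- **Missing-data step.** Section 5.6.1, Aim 1, models the probability of having an outcome and imputes within propensity strata. The reason given is "because we are relying on data available in the EHR, we anticipate more missing values than if this were an efficacy trial". The Aim 2 survey text does not refer back to it.

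**The concern.** A signed rank test needs both members of a pair. The planned analysis therefore describes patients who gave a baseline survey and also returned the follow-up in question, and the 6- and 12-month tests may rest on different patients. Reminders and gift cards can raise the return rate but do not correct for who returns.

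If the probability of return is linked to change in satisfaction, quality of life or social support, the mean change among returners differs from the mean change among all surveyed SMA participants. There is no surveyed comparison group in which the same selection could cancel. Benjamini-Hochberg deals with the number of tests, not with this bias. At stake is whether a significant Aim 2 change describes SMA participants or only those who answered twice.

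**Working it through.** **Inputs from the documents.** Minimum active-treatment sample 560 and maximum 1,568 (section 5.6.2); enrolment ceiling 1,100 (section 5.1.3). Check: 7 sites x 10 groups x 8 people = 560, and 7 x 16 x 14 = 1,568. (The same section's text speaks of 8 sites, which would give 640 and 1,792. That should be reconciled but does not affect this point.)

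**Assumptions, because the documents are silent.** Two-sided 0.05, so 2.5% of null tests fall on the improvement side; all 560 gave a baseline survey; patients independent; changes in SD units; true overall mean change zero. No survey return rate is stated. The only completion figure, 216/244 = 88.5%, is for A1c in the earlier trial.

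**Step 1: bias.** Suppose half the patients are engaged and change by +d, the rest by -d, with 80% and 50% returning.

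- Engaged returners: 280 x 0.8 = 224. Others: 280 x 0.5 = 140. Pairs: 364.
- Mean change among returners: d x (224 - 140)/364 = 0.231d, which is 0.046 SD at d = 0.2 and 0.069 SD at d = 0.3. The true value is 0.

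**Step 2: false improvement with the planned test.** With n = 364 and SD within subgroup 1, the SD among returners is sqrt(1 + d^2(1 - 0.231^2)), or 1.02 at d = 0.2 and 1.04 at d = 0.3. The standardised shift is bias x sqrt(364)/SD, times sqrt(3/pi) = 0.977 for the Wilcoxon test.

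- d = 0.2: 0.0462 x 19.08/1.02 x 0.977 = 0.84; P(Z > 1.96 - 0.84) = 13%.
- d = 0.3: 0.0692 x 19.08/1.04 x 0.977 = 1.24; P(Z > 1.96 - 1.24) = 24%.

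Simulation with 2,000 runs gave 14.1% and 22.6%; repeat runs put the second figure as high as about 25%. Hence about 14-25% against 2.5%. At N = 1,100 and d = 0.3 the simulated figure is 41.2%: a larger sample makes the false finding more likely, because the bias does not shrink.

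**Step 3: dependence on return rate and mechanism** (N = 560, simulated).

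| Mechanism | False improvement |
|---|---|
| 70% return, unrelated to change | 2.1% |
| 70% return, odds ratio 1.11 per SD of own change | 7.4% |
| 70% return, odds ratio 1.35 | 39.9% |
| 90% return, odds ratio 1.11 | 4.0% |
| 90% return, odds ratio 1.35 | 10.0% |
| about 70% return, low baseline scorers return more | 12.4-26.5% |
| about 70% return, high baseline scorers return more | 0.0-0.2% |

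The last two rows assume a baseline to follow-up correlation of 0.6. They show that the bias can also run against improvement and hide a real one.

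**Step 4: Benjamini-Hochberg.** With six tests, true change zero and return tied to a shared change factor (logit slope 0.5), at least one rejection occurred in 50.4% of runs, against 4.9% without selection.

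**Step 5: weighting by inverse probability of return.** In the Step 1 example the weights restore 224/0.8 = 280 and 140/0.5 = 280, so the weighted mean is (280d - 280d)/560 = 0. Simulated false improvement fell from 14.1% to 3.0% (d = 0.2) and from 22.6% to 2.2% (d = 0.3). Weighting fails if return depends on the unrecorded change itself. With about 70% return and odds ratio 1.35, the figure was 42% with and without weighting when engagement was uncorrelated with change, and fell only from 41% to 30% at a correlation of 0.4.

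**The case against.** - **The existing missing-data step may be meant to cover surveys.** It speaks of outcome data in general, and the same paragraph also covers utilization, which is an Aim 2 outcome. That is fair, but its stated reason is EHR data and the survey text does not invoke it. If surveys were intended, the plan should say so.
- **The direction is not known.** A reader might infer that engaged patients return more and that the result is tilted towards improvement. The documents do not show this, and Step 3 shows the opposite is possible. This stands.
- **Larger error rates are easy to quote.** A reader might fix the returners' shift at 0.10 SD with 60-70% return and read off rejection in 44-52% of trials. That is only the test's power at an assumed shift. Holding the gap between returners and non-returners at 0.25 SD instead gives about 31% at 70% return and 9% at 88.5%.
- **The correction data are not held for everyone.** Sections 5.2 and 5.3 bar linking surveys to record data until a HIPAA authorization is signed. Baseline A1c and other record items will be missing for some patients, possibly including many non-returners. This stands, and the fix must allow for it.
- **The aim is secondary and uncontrolled.** This also stands. Even perfect weighting would not turn a before-after change into an effect of SMAs. It limits the importance of the point but leaves the described change open to bias.

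**Conclusion.** The point holds in a conditional form. The plan's only survey analysis uses complete pairs, states no handling of unreturned surveys, and has no surveyed control group. If return is related to change, the result is biased for surveyed SMA participants, in either direction. Under the assumed selection of 80% versus 50% return by engagement, with subgroup changes of 0.2 to 0.3 SD, 560 surveyed and true overall change zero, false improvement is about 14-25% instead of 2.5%. It is near nominal if return is unrelated to change, and small near 90% return when selection is weak. Return rates, selection strength and alpha are assumptions, not figures from the documents.

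The documents do not support the stronger inferences that selective return will occur, that it will favour improvement, or that weighting would remove it fully. The point is worth acting on because the remedy is cheap and extends an approach the plan already uses.

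**What to change.** Extend the response-propensity approach of section 5.6.1 to the surveys:

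- Beside the paired Wilcoxon, report at 6 and at 12 months a mean change weighted by the inverse of the estimated probability of return, with a confidence interval that allows for SMA-group clustering (section 5.6.2 already accepts that group treatment induces it).
- Model return on baseline survey score, demographics and site for all patients, adding SMA attendance and baseline A1c where a signed HIPAA authorization permits linkage.
- Apply Benjamini-Hochberg to the weighted p-values.
- Report return rates, and baseline characteristics of returners and non-returners, at each time point.
- Add a delta-type sensitivity analysis that shifts the assumed mean change of non-returners over a stated range and reports where the conclusion changes.
- Describe unweighted results as change among respondents.

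The cost is SAP wording, some analyst time and slightly wider intervals; no new data collection is needed. Weighting corrects only for recorded predictors of return and does not replace the missing survey control group.

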### **5.6.1 Analysis Plans by Aim**

Aim 1 (Evaluation of the effect of SMAs and SMAs+P2P compared to usual care on diabetes patients' glycemic control, blood pressure, statin use, and insulin starts at 6 and 12-18 months post-enrollment): The primary analysis will be an intention to treat analysis (ITT) comparing all participants scheduled for an SMA (regardless of whether an SMA was actually attended) and eligible patients randomized to usual care. We also will conduct analyses comparing outcomes between the usual care group and: 1) The SMA Attendee group, defined as a subset of those in the SMA ITT group who attended at least one SMA; and 2) the SMA Engagement group, defined as the subset of patients who attended at least half of the SMAs offered in the series.

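### The group-randomised SMA versus SMA+P2P comparison can be dropped on an undefined participation condition, and the surveys have no between-arm test

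*Combined protocol and SAP*

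**What the plan says.** Section 5.1.1 has SMA and SMA+P2P groups run in random order within each site. It calls the comparison of these two arms the first analysis. Section 5.2 places a patient in an arm by the type of group that is starting. P2P itself is optional.

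Section 5.6.1 makes a different contrast primary: both SMA arms pooled against usual care. For SMAs it analyses by assignment, "comparing all participants scheduled for an SMA (regardless of whether an SMA was actually attended", and treats attendance-based comparisons as additional.

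Under Aim 2 the same section reports that "There were very few participants in the SMA+P2P group chose to be formally matched with another participant in their SMA". It continues: "If we do not have sufficient sample size of participants in P2P", then "we will be unable to compare outcomes between the SMA-only and SMA+P2P arms". In that event the investigators "will only conduct our primary analysis that combines the two SMA groups (SMA-only and SMA+P2P) into one active treatment group" and compare clinical outcomes with usual care. No number, decision time or decision-maker is given. The 560 in sections 5.2 and 5.6.2 is a minimum for the two SMA arms together, not a P2P threshold.

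For the surveys, section 5.1.1 gives comparison of SMA with SMA+P2P as the reason for collecting them. Section 5.6.1 says only that "we will conduct a paired Wilcoxon signed rank test to determine if there are significant changes between baseline" and each follow-up, with Benjamini-Hochberg control. The Mann-Whitney test under Aim 1 is for utilization measures. Section 5.3 rules out any contact with the usual-care controls, so they supply no survey data.

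**The concern.** The stated reason for dropping the comparison does not follow from the design. Because the offer of P2P is what was randomised, and arm membership does not depend on pairing, few pairs do not remove the comparison. They change what it estimates, namely the effect of offering P2P on top of SMAs, and they reduce power. The plan already accepts this reasoning for SMAs, where non-attenders stay in the analysis, but does not apply it to P2P.

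Two things are at stake. First, section 5.6.2 sizes the study for this contrast at 0.5 A1c points, the benefit that clinical managers said they would need before adopting a new strategy. If the clause is invoked, the only group-randomised evidence on offering P2P goes unreported. Second, if the arm comparison is dropped, the survey outcomes have no comparator, since the fallback covers clinical outcomes only. A before-after change cannot separate a programme effect from drift over time, so it cannot show the impact that Aim 2 asks about. Even if the clause is never invoked, no between-arm survey test is named.

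**Working it through.** **Inputs from section 5.6.2.** SD of A1c change 1.45; ICC 0 to 0.10; target difference 0.5 points; 10 to 16 groups per site, split equally between arms; 8 to 14 patients per group.

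**Assumptions.** Two-sided alpha 0.05 (not stated in the plan) and complete A1c unless noted. Uptake is described only as very few, so 50%, 25% and 10% are illustrative. Patients who pair are assumed to gain 0.5 points.

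**Formulas.** With k groups per arm, m patients per group and n = k × m per arm:

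- design effect = 1 + (m − 1) × ICC
- SE of the arm difference = 1.45 × √(2 × design effect / n)
- 95% half-width = t(0.975; 2k − 2) × SE
- power from the non-central t with 2k − 2 degrees of freedom, an approximation to the plan's Satterthwaite F test.

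**The plan's own figures.** Section 5.6.2 claims power of 0.8 at 10 groups per site, except with 10 patients per group and ICC 0.10. With 5 sites (25 groups per arm) and ICC 0.10, power is 0.782, 0.815 and 0.838 at 10, 12 and 14 per group. Only the excepted case falls below 0.8, so the statement reproduces. The minimum of 560 needs 7 sites: 7 × 10 × 8 = 560, or 35 groups per arm. The same section speaks of 8 sites, which gives 40 per arm. All three counts are shown.

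**Precision, at any uptake (m = 8, ICC 0.10).** Design effect = 1 + 7 × 0.10 = 1.7. For k = 35, n = 280, SE = 1.45 × √(3.4/280) = 0.160 and the half-width is 1.995 × 0.160 = 0.32.

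| Groups per arm | 95% half-width (A1c points) |
|---|---|
| 15 | 0.50 |
| 25 | 0.38 |
| 35 | 0.32 (0.24 at ICC 0) |
| 40 | 0.30 |

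**Power and exclusion.** The effect of the offer is 0.5 × u + g × (1 − u), where u is uptake and g is the gain in unpaired patients. With g = 0 it is 0.25, 0.125 and 0.05 points at 50%, 25% and 10% uptake. Benefit is the chance of a significant result favouring P2P. Exclusion is the chance that the upper confidence limit falls below 0.5.

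| Scenario | Quantity | 50% | 25% | 10% |
|---|---|---|---|---|
| 35 groups, g = 0 | benefit | 0.338 | 0.117 | 0.049 |
| 35 groups, g = 0 | exclusion | 0.338 | 0.638 | 0.793 |
| 25 groups, g = 0 | benefit | 0.253 | 0.095 | 0.044 |
| 25 groups, g = 0 | exclusion | 0.253 | 0.494 | 0.645 |
| 35 groups, g = 0.1 | exclusion | 0.234 | 0.457 | 0.603 |
| 35 groups, g = 0.2 | exclusion | 0.150 | 0.284 | 0.384 |
| 35 groups, g = 0, 20% missing | exclusion | 0.305 | 0.585 | 0.742 |
| 25 groups, g = 0, 20% missing | exclusion | 0.229 | 0.447 | 0.592 |

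At full uptake with 35 groups, power is 0.870. Values of g above zero are included because unpaired patients may still attend the first P2P visit and the drop-in sessions. Missing data are included because, in the plan's words, "we anticipate more missing values than if this were an efficacy trial". Twenty per cent missing leaves 6.4 per group and a design effect of 1 + 5.4 × 0.10 = 1.54; the half-widths become 0.34 (35 groups) and 0.40 (25 groups).

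**Surveys.** No arithmetic applies. The stated purpose is a comparison between arms, the only named test is within patients, and the only other study group has no survey data.

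**The case against.** The strongest reply is that the contrast may carry little information. If very few means something near 10%, power to show benefit is about 4% to 5%, and an interval that excludes 0.5 then largely restates low uptake. With 25 groups per arm, 20% missing A1c and a 0.1-point gain in unpaired patients, the exclusion chance at 10% uptake falls to 42%. Deciding not to rely on such a comparison is a defensible feasibility judgement. This stands as a limit on what the analysis can deliver, but it justifies cautious reporting of the estimate and its interval, not omission.

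Secondly, the condition might refer to too few P2P groups having run, in which case it is an ordinary feasibility caveat. That reading is possible, although the preceding sentence about pairing points to uptake. Either way the threshold is missing.

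Thirdly, recruitment safeguards are better than a focus on scheduling suggests. Sections 5.1.1 and 5.2 specify random sampling for invitation and an identical script for both group types. Section 5.2 states that the scheduler is unaware of group type for referrals but not for the data pull, so baseline balance is still worth reporting.

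Finally, nothing here shows selective reporting. The condition is worded in terms of participation, not outcomes. But with no decision time or decision-maker, the documents cannot settle when or with what knowledge it would be applied.

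**Conclusion.** The concern holds and should be fixed. The clause gives a participation-based reason, with no threshold, for omitting a comparison that the randomisation supports at any uptake. Separately, the surveys lack any between-arm analysis despite being collected for one. Pooled SMA versus usual care remains primary and is not affected.

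Under the plan's SD and worst-case ICC with 8 per group, the offer of P2P would be estimated to within about ±0.30 to ±0.38 A1c points with 25 to 40 groups per arm. Precision reaches ±0.50 at about 15 groups per arm, which is roughly where the comparison stops being useful against the 0.5-point target. Power to show benefit is low at low uptake; the value lies in bounding the effect of the offer. These sizes rest on assumed uptake, the assumed gain in pairs and the assumed alpha. The documents do not report groups run or surveys returned by arm. The absence of a threshold and of a survey test rests on the text alone.

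**What to change.** - Replace the conditional clause with a commitment to report SMA versus SMA+P2P as a secondary analysis, by the arm each group was randomised to, for both record-based and survey outcomes.
- Allow for clustering by SMA group. The Aim 1 model in section 5.6.1 lists random intercepts for patient and site only, so a group-level term has to be added for this comparison.
- Label the result as the effect of offering P2P. Report groups per arm, uptake, baseline balance and the confidence interval, and make no claim about effect in those who used P2P.
- If a feasibility condition is kept, state it as a number of groups per arm, not as uptake.
- For the surveys, name a between-arm analysis that accounts for baseline and SMA group, such as a baseline-adjusted mixed model or a clustered rank test on change. Keep Benjamini-Hochberg across scales and present within-arm change as descriptive.
- Keep pooled SMA versus usual care as primary, and reconcile section 5.1.1, which calls the two-arm comparison the first analysis, with section 5.6.1.

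The cost is wording, since sections 5.1.1 and 5.5 already provide for these data in both SMA arms. The downside is that the secondary result may be imprecise, and it is informative only if enough groups ran in each arm.
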